6.2. Method of Treatment Assignment

Patients who meet all criteria for enrollment will be randomized to double-blind treatment at Visit 3. Assignment to treatment groups will be determined by a computer-generated random sequence using an interactive web-response system (IWRS). The IWRS will be used to assign double-blind investigational product to each patient. Site personnel will confirm that they have located the correctly assigned package by entering the confirmation number found on the package into the IWRS.

To achieve between-group comparability, the randomization will be stratified by country, acute headache medication overuse (yes/no), and use of concurrent migraine prophylactic medication (yes/no). Acute headache medication overuse will be determined during the prospective baseline period. Acute headache medication overuse criteria will be adapted from Section 8.2 of the ICHD-3 beta guidelines (ICHD-3 2013). To ensure an appropriate balance of patients with concomitant prophylaxis use, the sponsor will stop enrollment of patients with concomitant prophylaxis use if the number of patients exceeds approximately one-third.

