9.4.2. Key Secondary Analyses

The key secondary objectives (see Table CGAI.1) will be tested using an appropriate multiple testing approach providing strong control of the familywise error rate (for the primary and key secondary tests) at a one-sided 0.025 alpha level (or, equivalently, two-sided 0.05 alpha level).

There will be no adjustments for multiplicity for analyses of other endpoints. If the multiple testing approach for key secondary measures only needs to be changed, the updated approach will be provided in the SAP, and it should not lead to modification of this protocol.

The key secondary measures will be analyzed for the double-blind treatment (Study Period III).

For the continuous key secondary measures, the change from baseline will be analyzed from repeated measures analyses as described in Section 9.4.1. For the categorical key secondary efficacy measure of 50%, 75%, and 100% response, the percentage of patients meeting response criteria during the 3-month double-blind treatment phase will be estimated for each treatment from a categorical, pseudo-likelihood-based repeated measures analysis of longitudinal binary

outcomes indicating whether patients meet response criteria. This analysis will be implemented using the GLIMMIX procedure in SAS.

If the sample size is increased, the CHW test statistic will be calculated for the primary and all the key secondary outcomes before applying the multiple testing procedure.

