5.3. Randomization and Treatment Assignment

Patients will be randomized in a 2:1:1 ratio to placebo, LY2951742 120 mg/month, or 240 mg/month. Randomization will be stratified within country and by acute headache medication overuse (yes versus no), and use of concurrent migraine prophylactic medication (yes versus no).

^a Patients randomized to the 120 mg dose will receive a loading dose of 240 mg at the first injection only (Visit 3).

^b At Visit 7, all patients who enter the open-label extension will receive LY2951742 at a dose of 240 mg.

^c At Visit 8, all patients will receive LY2951742 at a dose of 120 mg.

d Starting at Visit 9, patients will have the option to receive either LY2951742 dose of 120 mg or 240 mg (flexible dosing).

The acute headache medication overuse will be based on the frequency of acute headache medication intake during the 30-day baseline, and will be adapted from Section 8.2 of the ICHD-3 beta guidelines (ICHD-3 2013).

To ensure an appropriate balance of patients with concurrent prophylaxis use, the sponsor will stop enrollment of patients with concurrent prophylaxis use if the number of patients exceeds approximately 1/3.

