5.5.1.1. Adjustments for Covariates

The MMRM models will include the fixed, categorical effects of treatment, pooled country, month, baseline medication overuse (yes versus no), concurrent prophylaxis (yes versus no), and treatment-by-month interaction, as well as the continuous, fixed covariates of baseline value and baseline value-by-month interaction. The baseline value and baseline-by-month interaction are included to account for the differential influence over time that the baseline value has on the postbaseline values. Rules for pooling countries are defined in Section 5.5.1.3. Pooled country will be excluded in MMRM models for safety measures.

When an ANOVA model is used to analyze a continuous efficacy variable, the model will contain the main effects of treatment, baseline medication overuse (yes versus no), concurrent prophylaxis use (yes versus no) and pooled country. When an ANCOVA model is used to analyze a continuous efficacy variable, the model will contain the main effects of treatment, baseline medication overuse (yes versus no), concurrent prophylaxis use (yes versus no) and pooled country, and appropriate baseline value as a covariate. When an ANOVA or ANCOVA model is used to analyze a continuous safety variable, pooled country will be removed from the model.

The GLIMMIX models for the repeated binary outcomes will include the fixed, categorical effects of treatment, month, baseline medication overuse (yes versus no), concurrent prophylaxis (yes versus no), and treatment-by-month interaction, as well as the continuous, fixed covariate of baseline value. Pooled country and the baseline value-by-month interaction will be excluded from the model in order to increase the likelihood of convergence.

When a logistic regression is used to analyze a binary variable, the model will include the main effect of treatment, baseline medication overuse (yes versus no), concurrent prophylaxis use (yes versus no) and pooled country, and appropriate baseline value as a covariate. Pooled country may be excluded from the model in case of non-convergence.

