To assess the robustness of the MMRM results to deviations from normality assumption, a sensitivity analysis for raw number of migraine headache days (total number of migraine headache days for each interval without normalization to 30-day period) will be conducted with a repeated measures negative binomial regression model fitted with SAS PROC GLIMMIX. The model will include treatment, pooled country, month, baseline medication overuse (yes versus no), concurrent prophylaxis use (yes versus no) and treatment-by-month interaction, as well as the continuous fixed covariates of baseline number of monthly migraine headache days and baseline-by-month interaction, log (number of compliant days within each month/30) as the offset in the model. In case of non-convergence, pooled country and/or baseline-by-month interaction may be excluded from the model. Directional consistency of treatment effects from this model and the primary analysis MMRM model as specified in Section 5.5.10.1 will be examined.

In addition, as another form of sensitivity analysis, residuals from the primary analysis MMRM model will be examined and outliers identified. Consistency of results before and after removing patients with outlier residuals will be examined.

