5.5.10.3. Secondary and Exploratory Efficacy Analyses

Key secondary efficacy measures will be tested with adjustment for multiple testing as specified in Section 5.5.10.4.

Other planned secondary and exploratory efficacy analyses will be conducted without multiplicity adjustment. Table CGAI.5.5 summarizes all the planned (unadjusted) secondary and exploratory efficacy analyses for SP III, SP III/IV, and SP III/IV/V, additional statistical analysis details are also provided below.

Continuous Secondary Efficacy Measures

For the continuous secondary efficacy measures, the change from baseline to each postbaseline period will be estimated for each treatment from repeated measures analyses as described for analysis for primary outcome.

For the continuous secondary efficacy measures where the objective is to assess overall mean change during 3 month double-blind treatment phase, the endpoint for each LY2951742 dose arm compared with placebo will be estimated as the treatment main effect from the MMRM analysis assessing the average treatment effect across Months 1, 2, and 3.

In addition to the repeated measures analyses, the mean change from baseline to average monthly measures during the 3-month treatment phase or LOCF endpoint in SP III will be estimated for the continuous efficacy measures using ANCOVA models with covariates adjustment described in Section 5.5.1.1.

Binary Efficacy Measures

For the repeated binary efficacy measures such as responder indicators based on the number of migraine headache days, the visit wise binary outcomes indicating whether patients meet X% response criteria will be analyzed using a categorical, pseudo-likelihood-based repeated measures analysis. This analysis will be implemented using the GLIMMIX procedure in SAS to compare treatments and include the fixed, categorical effects of treatment, month, baseline medication overuse (yes versus no), concurrent prophylaxis (yes versus no), and treatment-bymonth interaction, as well as the continuous, fixed covariate of baseline value.

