An unstructured covariance structure will be used to model the within-patient errors (denoted by TYPE=CHOL in the RANDOM statement). The Newton-Raphson method with ridging will be used for nonlinear optimization (denoted by including NLOPTIONS TECH=NRRIDG). The Kenward-Roger approximation will be used to estimate denominator degrees of freedom. If the model does not converge, the Fisher's scoring algorithm will be utilized by the SCORING option in SAS.

If the model still fails to converge, the model will be fit using covariance matrices in the following order specified by a decreasing number of covariance parameters until convergence is met:

- Heterogeneous Toeplitz,
- Heterogeneous autoregressive,

- Toeplitz, and
- Autoregressive.

If necessary, both fitting algorithms will be used in the pre-specified order before proceeding to the next covariance structure in the sequence.

For models where the unstructured covariance matrix is not utilized, the sandwich estimator (Diggle et al. 1994) will be used to estimate the standard errors of the fixed effects parameters. The sandwich estimator is utilized by the EMPIRICAL option in SAS. When the sandwich estimator is utilized, the Kenward-Roger approximation for denominator degrees of freedom cannot be used. Instead, the denominator degrees of freedom will be partitioned into between-subject and within-subject portions by the DDFM=BETWITHIN option in SAS.

For the binary secondary efficacy measures where the objective is to assess proportion of patients with X% response during the 3-month double-blind treatment phase, the endpoint for each LY2951742 dose arm compared with placebo will be estimated as the treatment main effect from the categorical MMRM analysis assessing the average response rate across Month 1, Month 2, and Month 3.

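### The 50%, 75% and 100% response models leave out pooled country, a randomization stratum, in all cases, where the SAP's logistic and negative binomial models may drop it only on non-convergence

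*SAP*

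**What the plan says.** Protocol 6.2 and SAP 5.3 both stratify randomization by country, acute medication overuse and concurrent prophylaxis. The primary MMRM (SAP 5.5.10.1) adjusts for all three, with small countries pooled under SAP 5.5.1.3.

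For the repeated binary models, SAP 5.5.1.1 states: "Pooled country and the baseline value-by-month interaction will be excluded from the model in order to increase the likelihood of convergence". SAP 5.5.10.3 repeats the term list without country and, for response over the three months, adds that "the endpoint for each LY2951742 dose arm compared with placebo will be estimated as the treatment main effect from the categorical MMRM analysis". Protocol 9.4.2 places these endpoints among the key secondaries ("For the categorical key secondary efficacy measure of 50%, 75%, and 100% response"). It names GLIMMIX but lists no covariates.

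Other models are treated differently. Of logistic regression, SAP 5.5.1.1 says: "Pooled country may be excluded from the model in case of non-convergence". Of the negative binomial sensitivity analysis, SAP 5.5.10.2 says: "In case of non-convergence, pooled country and/or baseline-by-month interaction may be excluded from the model". SAP 5.5.11 has an equivalent rule for health care utilization.

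The responder model also has its own convergence sequence in 5.5.10.3: Fisher scoring, then four simpler covariance structures.

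**The concern.** An analysis normally carries the factors used to stratify randomization unless there is a reason not to. The only reason given here is convergence, and the SAP treats that as a contingency for comparable models. For the responder models it is assumed in advance, at every response threshold, and the SAP reports no evidence of trouble at 50% or 75% response with about 1140 patients.

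One visible result is that 50% response sustained over all three months (logistic) is adjusted for country, while the key secondary 50% response is not. What is at stake is some precision on endpoints inside the multiplicity procedure.

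**Working it through.** **1. The models side by side**

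| Analysis | SAP section | Pooled country |
|---|---|---|
| Primary MMRM | 5.5.10.1 | included |
| Logistic, e.g. sustained 50% response | 5.5.1.1, 5.5.10.3 | included; may be dropped on non-convergence |
| Negative binomial, sensitivity of primary | 5.5.10.2 | included; may be dropped on non-convergence |
| Negative binomial, health care utilization | 5.5.11 | included; may be dropped on non-convergence |
| Ordinal GLIMMIX, weekly days in Month 1 | 5.5.10.3 | included; no dropping rule |
| Binary GLIMMIX, 50%, 75%, 100% response | 5.5.1.1, 5.5.10.3 | excluded in all cases |

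**2. The plan's own figure**

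The only power statement is for the primary endpoint (SAP 5.2: 1140 patients, 2:1:1, effect size 0.30, 15% dropout, about 95%). Completers are 570 × 0.85 = 484.5 and 285 × 0.85 = 242.25. The standard error is √(1/484.5 + 1/242.25) = 0.0787, and the Dunnett critical value at one-sided 0.025 with correlation 1/3 is 2.227. Power is Φ(0.30/0.0787 − 2.227) = 94.4% for one dose, which agrees. No corresponding figure exists for the responder endpoints, so the rest is illustrative.

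**3. Power with and without country**

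From the documents: 1140 patients, 2:1:1, 11 planned countries (Protocol 9.1). Assumed: unequal country sizes, placebo response, odds ratio and between-country SD on the logit scale. Each setting used 2000 trials with country-stratified blocks of four. One dose was compared with placebo on a single binary outcome by logistic regression at one-sided 0.025. Entries are power (%) without / with country, then the loss in points.

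| Placebo response (OR) | SD 0 | SD 0.3 | SD 0.6 | SD 1.0 |
|---|---|---|---|---|
| 5% (2.2) | 81.35 / 82.05; 0.70 | 81.05 / 81.80; 0.75 | 83.10 / 83.70; 0.60 | 82.10 / 83.65; 1.55 |
| 15% (1.7) | 80.70 / 81.20; 0.50 | 81.85 / 82.25; 0.40 | 79.50 / 80.60; 1.10 | 75.40 / 79.45; 4.05 |
| 25% (1.6) | 83.40 / 83.65; 0.25 | 82.80 / 83.60; 0.80 | 80.35 / 82.35; 2.00 | 73.95 / 78.95; 5.00 |

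At SD 0 country carries no information, yet differences of 0.25 to 0.70 appear, so differences of that size cannot be credited to adjustment. A smaller simulation (12 countries, 570 against 285, 15% placebo response, OR 1.73, up to 600 trials per setting) gave 85.7 / 86.0, 84.5 / 85.5 and 82.7 / 84.9 at SD 0.3, 0.5 and 0.7. Those are losses of 0.3, 1.0 and 2.2 points.

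To read the scale: a country one SD above average has response odds multiplied by e^0.3 = 1.35, e^0.7 = 2.0 or e^1.0 = 2.7.

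**4. Type I error**

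Under no effect, the same 12 settings gave 0.020 to 0.030 without country and about 0.022 to 0.031 with it. The Monte Carlo standard error is √(0.025 × 0.975/2000) = 0.0035. The lowest value, 0.020, is (0.025 − 0.020)/0.0035 = 1.4 standard errors below nominal.

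**5. Sparse countries**

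The pooling rule in SAP 5.5.1.3 lets a country stand alone with 4 + 2 + 2 = 8 patients. Assume a monthly 100% response rate of 2% to 5% (the documents give none). The chance of no responder in any of three months is (1 − p)^24 if months are independent: 0.98^24 = 62% and 0.95^24 = 29%. If months are fully dependent it is (1 − p)^8: 0.98^8 = 85% and 0.95^8 = 66%. A fixed effect for such a country could not be estimated.

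**The case against.** The exclusion is prespecified and reasoned, the other two strata and the baseline value stay in the model, and nothing in the protocol is contradicted. The planned model is a three-month pseudo-likelihood fit with unstructured covariance and Kenward-Roger degrees of freedom, which is harder to fit than a single logistic regression. If it fails, 5.5.10.3 leads to simpler covariance structures and, with them, the sandwich estimator, so leaving country out protects the preferred analysis. The models that keep country are not among the key secondary analyses, and for multiplicity-controlled tests one fixed covariate set is arguably the stricter prespecification.

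Much of this stands. Convergence was not tested here, so it cannot be said that 50% and 75% response would converge with country; the SAP simply gives no evidence that they would not. For 100% response the worry is legitimate (step 5). Matching the primary is not a good argument either, because the responder model also omits the baseline-by-month term.

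It does not justify a blanket rule. If country is dropped before any other fallback, a failed fit returns to exactly the current model, with unstructured covariance still available.

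A reader might go further and infer that omitting a stratum inflates error or makes the tests conservative. Neither is shown: type I error was near nominal in every setting. Nor is the smaller log odds ratio without country (about 1% to 14% lower across the settings) evidence of bias. It partly reflects a less conditional quantity.

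**Conclusion.** The inconsistency is real and minor. Pooled country is removed in advance from the responder key secondary models, while the SAP makes its removal contingent on non-convergence for the logistic and negative binomial models. Validity is not affected.

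The likely cost is about 0 to 2 points of power at a between-country SD of 0.3 to 0.7. The 4 to 5 points seen at SD 1.0 need very large country differences and should not be quoted as the expected loss.

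All of this rests on assumed response rates, odds ratios and country variation, and on one binary outcome standing in for three repeated months. The simulations also left out baseline migraine days, overuse and prophylaxis, which the SAP keeps and which could absorb part of the country effect. SAP 5.5.10.4 is not in the text available, so the alpha reaching each responder test, and hence the practical consequence, cannot be assessed; one-sided 0.025 was used.

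**What to change.** In SAP 5.5.1.1 and 5.5.10.3, fit the 50% and 75% response models with pooled country as a fixed effect. If a model does not converge, remove pooled country as the first prespecified step, before Fisher scoring and the covariance sequence. That returns to the model as now written. Word the step as mandatory rather than permissive, and state that a country effect that cannot be estimated for lack of responders counts as non-convergence. The 100% response model may stay without country, and the exclusion of baseline-by-month need not change.

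The cost is a few lines of SAP text and one more fallback step, settled before the study team is unblinded. The drawback is that the adjustment set may differ between thresholds, so the report should say which model was used for each. If the sponsor prefers one common model, keep the current text and add a prespecified country-adjusted sensitivity analysis for 50% and 75% response.

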5.5.1.2. Handling of Dropouts or Missing Data

Two statistical approaches to handling missing data will be used as appropriate: repeated measures analyses and ANCOVA/ANOVA model using change from baseline to the average of observed monthly measures during the 3-month treatment phase (for measures with objectives evaluated during the entire 3 months of treatment phase) or LOCF endpoint (for measures with objectives evaluated at Month 3).

For the repeated measures analyses, the model parameters are simultaneously estimated using restricted likelihood estimation incorporating all of the observed data. Estimates have been shown to be unbiased when the missing data are missing at random.

Please refer to Section 5.4.1 for approach to handling missing diary data for derivation of migraine headache days and other efficacy measures (with the exception of migraine attacks) derived from ePRO data per 30-day period.

Approaches to handling missing diary data for the derivation of migraine attack

For the analysis of migraine attack, the LOCF method will be used to impute the missing ePRO diary days. In other words, if the patient was migraine headache free on the day before the missing ePRO diary day, this would be carried forward as no migraine headache day until the actual next non-missing diary day. On the other hand, if the day before the missing ePRO diary day is a migraine headache day, then it would be carried forward as migraine headache day until the next non-missing diary day. The imputation will be carried out for all the missing diary days between the first non-missing to the last day during that period.

If the compliance rate for a monthly interval is \leq 50%, the number of monthly migraine attacks during that month will be considered missing. Please refer to Section 5.5.7 for compliance rate calculation.

5.5.1.3. Rules for Pooling Countries

All countries with fewer than 4 randomized patients for placebo arm or fewer than 2 patients for any LY2951742 arm with baseline and at least 1 postbaseline migraine headache day's value will be pooled together within region and considered a single country for analyses.

All analyses will use pooled country when applicable. The investigative site numbers will be included in the listings.

5.5.1.4. Analysis Populations

There were 4 analysis populations defined:

Intent-to-Treat (ITT) Population: All patients who are randomized and receive at least 1 dose of study drug.

Safety Population: This population is the same as the ITT population defined above.

Open-label treatment population: All patients who enter the open-label treatment phase (Study Period IV) as indicated by receiving any injections starting from V isit 7. Patients in the open-label treatment population will be analyzed as a single group as they start with the same dose in the study period. Analyses for open-label phase only will be based on open-label treatment population.

Post-treatment Population: All patients who enter the post-treatment phase (Study Period V) as indicated by entering any post-treatment visit (telephone or office visit). Analyses for post-treatment phase only (that is, excluding earlier study periods) will be based on post-treatment population.

Unless otherwise stated, all analyses will be analyzed according to the ITT principle on the ITT population. That is, patients will be analyzed according to the treatment they were randomized to, regardless of whether they actually received a different treatment.

Safety analyses (Section 5.5.1.2) and analyses for disposition and exposure will be conducted based on the modal treatment group patients have received (Placebo, LY120mg, or LY240mg) during the double-blind Study Period from the first to last injections at Visit 3 through Visit 6. For determining modal dose, do not consider the loading dose visit for subjects assigned to an LY120mg treatment group; do consider it for subjects assigned to the Placebo and LY240mg treatment groups. If there are 2 or more modes, then add the loading dose visit and recalculate the mode, if any. If a tie still remains, the highest LY dose of the modes will be used.

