To avoid biased reporting, patients must not be told the number of headache days or migraine headache days on which study qualification is based.

Study Period III: At the start of the 3-month double-blind treatment phase (Visit 3), patients meeting all eligibility requirements will be randomized to 1 of 3 treatment groups in a 2:1:1 ratio to receive placebo, 120 mg/month LY2951742, or 240 mg/month LY2951742, respectively. At Visit 3, if available and where local regulations and Ethical Review Boards allow, patients will also watch a training video designed to address patient expectations with regard to participation in a placebo-controlled trial and the difference between medical treatment and research. To preserve blinding throughout the study, patients in all treatment groups will receive 2 injections of investigational product at each dosing visit (two placebo injections, two 120-mg LY2951742 injections, or one placebo injection and one 120-mg injection). Patients randomised to the 120-mg dose of LY2951742 will receive an initial loading dose of 240 mg (2 injections of 120 mg each).

The patient will be considered enrolled in the study when randomization occurs. During this phase, study procedures at dosing visits must always occur prior to the patient receiving their assigned treatment.

Patients will be given investigational product (LY2951742 or placebo) injections during office visits (Figure CGAI.1). For all treatment groups, investigational product is administered by subcutaneous injection once monthly at the dosing visits. At Visit 3 (first dose), patients are required to remain in the office for observation for 30 minutes post injection. Patients will continue to log in and complete the ePRO diary each day. Patients may continue to take their allowed acute migraine headache medication (with some limitations; see Section 6.8) during the treatment phase.

Patients will receive their last double-blind dose of investigational product at Visit 6. Patients who do not opt to continue into Study Period IV will receive no further injections and will proceed directly to the post-treatment follow-up phase.

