4.3. Scientific Rationale for Study Design

The length of the randomized, double-blind treatment phase (3 months) is considered a sufficient duration to assess the safety and efficacy of a migraine prevention medication given the mechanism and observed onset of action for CGRP antibodies (Dodick et al. 2014a, 2014b). Furthermore, a placebo-controlled study with a duration longer than 3 months may not be tolerated by patients suffering from chronic migraine. A 4-month post-treatment follow-up phase is included to evaluate patient safety during wash-out of LY2951742. This allows for a total of 5 months of observation from the time of last injection of LY2951742. A 5 -month post-treatment observation period allows for a wash-out of approximately 5 elimination half-lives of LY2951742 and should decrease LY2951742 serum concentrations by approximately 97% during this time.

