6.1. Treatments Administered

This study involves a comparison of LY2951742 (120 and 240 mg) administered once monthly with placebo. Sites will administer injections of LY2951742 or placebo at 3 office visits during the double-blind treatment phase and LY2951742 at 9 office visits during the open-label treatment phase (Appendix 2). During the double-blind treatment period, 2 injections of investigational product (LY2951742 and/or placebo) will be given at each dosing visit to preserve blinding.

Possible injection sites include the abdomen, thigh, and upper arm. Buttocks may also be used, if needed.

The investigator or his/her designee is responsible for the following:

- maintaining accurate records of investigational product dispensing
- at the end of the study returning all unused medication to Lilly, or its designee, unless the sponsor and sites have agreed all unused medication is to be destroyed by the site, as allowed by local law.

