9.2. General Statistical Considerations

Statistical analysis of this study will be the responsibility of Lilly or its designee. Details of statistical analysis methods will be described in the statistical analysis plan (SAP) document.

Unless otherwise specified, analyses will be conducted on an intent-to-treat (ITT) population, which will include all patients who are randomized and receive at least one dose of investigational product. Patients in the ITT population will be analyzed according to the treatment group to which they are randomized. When change from baseline is assessed, the patient will be included in the analysis only if he/she has a baseline and a postbaseline measurement.

Randomization will be stratified based on the frequency of acute headache medication intake during the 30-day baseline as yes/no overuse of acute headache medications. In addition, concomitant prophylaxis use will also be stratified.

For some of the analyses of the open-label treatment phase (Study Period IV), the open-label treatment population will be used. Open-label treatment population will be defined as all patients who entered the open-label treatment phase as indicated by receiving study drug at Visit 7. Patients in the open-label treatment population will be analyzed according to the treatment to which they were randomized in the double-blind period (Study Period III), as appropriate.

The primary analyses will be performed using a restricted maximum likelihood-based mixed models repeated measures (MMRM) technique with prespecified model terms (Section 9.4.1).

Visitwise binary efficacy variables will be analyzed using a generalized linear mixed model (GLIMMIX) as pseudo-likelihood-based mixed effects repeated measures analysis.

In addition to the MMRM approach, analysis of covariance (ANCOVA) model or analysis of variance (ANOVA) with the last-observation-carried-forward (LOCF) will also be implemented. When an ANCOVA model is used to analyze a continuous variable, the model will contain the main effects of treatment and pooled country, baseline medication overuse (yes/no), concomitant prophylaxis use (yes/no), as well as the continuous fixed covariates of baseline. The ANOVA model will use the same terms except the continuous fixed covariates of baseline. Type III sum-of-squares for the least-squares means will be used for the statistical comparisons.

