5.5.12.1. Categorical Safety Variables

Unless specified otherwise, the categorical safety analyses will include both scheduled and unscheduled visits. Categorical safety analyses will only be conducted for SP III, SP IV, SP V, and SP III/IV separately.

Comparisons between treatment groups for all categorical safety measures will be made using CMH test for SP III, and SP III/IV with the ITT population.

Descriptive statistics only will be presented for the treatment groups in SP IV and SP V.

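### The SAP's single-group rule for the open-label phase conflicts with its other sections, and the reason given (same starting dose) ignores that about half the group is drug-naive at Visit 7

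*SAP*

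**What the plan says.** SAP 5.5.1.4 defines the open-label treatment population, bases open-label-only analyses on it, and says these patients "will be analyzed as a single group as they start with the same dose in the study period". It gives no other reason for pooling.

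Other text points the other way:

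- SAP 5.5.12.1 (categorical safety): "Descriptive statistics only will be presented for the treatment groups in SP IV and SP V". SAP 5.5.2 (disposition) and 5.5.9 (concomitant therapy) say the same in substance.
- SAP 5.5.10.3 plans a logistic regression with a treatment term for sustained 50% response in SP IV, among patients previously given LY2951742.
- A later paragraph of SAP 5.5.1.4 assigns safety, disposition and exposure analyses to the modal double-blind group (placebo, 120 mg or 240 mg). It does not exempt SP IV.
- Protocol 9.2: "Patients in the open-label treatment population will be analyzed according to the treatment to which they were randomized in the double-blind period". That sentence ends with the qualifier that this is done as appropriate, and its paragraph concerns only some of the open-label analyses.

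SAP Table CGAI.5.4 sets the SP IV baselines. For treatment-emergent adverse events (TEAEs) and laboratory values they are all of Visits 1 to 7. For blood pressure, pulse and ECG they are the last non-missing value in Visits 1 to 7. Serious adverse events and discontinuations due to adverse events have no baseline.

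**The concern.** All patients do receive 240 mg at Visit 7, but they arrive with different histories. Former active patients have had up to three monthly doses and still carry drug. Former placebo patients have had none.

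The baselines add a second difference. An event that a former active patient already had on drug in SP III counts in SP IV only if it worsens. A former active patient whose laboratory value became abnormal on drug leaves the at-risk set for that direction. The last blood pressure, pulse or ECG value before SP IV is an on-drug value for former active patients and a drug-free value for former placebo patients. The same column heading would therefore mean different things by prior arm.

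At stake is the reading of the SP IV safety tables. A single incidence for, say, injection-site or hypersensitivity events would describe neither first nor continued exposure. A programmer also cannot tell from the SAP which layout to produce.

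**Working it through.** **1. The plan's own figure.** Protocol 4.3 says a 5-month observation period "allows for a wash-out of approximately 5 elimination half-lives of LY2951742" and "should decrease LY2951742 serum concentrations by approximately 97% during this time". Check: 1 − 0.5^5 = 96.9%, which agrees. The implied half-life is 5 months / 5 = 1 month, taken here as 30 days.

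**2. Drug on board at Visit 7.** Inputs:

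- Three double-blind doses (protocol 6.1: "Sites will administer injections of LY2951742 or placebo at 3 office visits during the double-blind treatment phase"), given monthly.
- In the 120 mg arm: 240, 120, 120 mg (protocol 4.1: "Patients randomised to the 120-mg dose of LY2951742 will receive an initial loading dose of 240 mg"). In the 240 mg arm: 240, 240, 240 mg.
- 240 mg for everyone at Visit 7.

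Assumptions: linear one-compartment kinetics, immediate full absorption, exact 30-day intervals. Load = sum of dose × 0.5^(months elapsed).

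- Former 120 mg, before Visit 7: 240 × 0.125 + 120 × 0.25 + 120 × 0.5 = 120 mg.
- Former 240 mg, before Visit 7: 240 × (0.125 + 0.25 + 0.5) = 210 mg.
- Former placebo: 0 mg.

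After adding 240 mg, the loads are 240 mg (placebo), 360 mg (120 mg; 360/240 = 1.50, +50%) and 450 mg (240 mg; 450/240 = 1.875, +88%). With half-lives of 25 to 35 days, the excess for the former 240 mg arm runs from +71% to +103%.

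**3. How long the difference lasts.** Everyone receives 120 mg at Visit 8. From Visit 9 dosing is flexible, and 120 mg is assumed here. The excess over former placebo just after each dose is:

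| After visit | Former 120 mg | Former 240 mg |
|---|---|---|
| 7 | +50% | +88% |
| 8 | +25% | +44% |
| 9 | +12.5% | +22% |
| 10 | +6% | +11% |
| 12 | under 2% | under 3% |

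Visit 8 check: 450 × 0.5 + 120 = 345 mg, against 240 × 0.5 + 120 = 240 mg; 345/240 = 1.44.

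**4. Drug-naive share.** SAP 5.2 plans 570 / 285 / 285, so 570/1140 = 50% with equal dropout. If dropout were 20% on placebo and 10% on active drug: 456/(456 + 513) = 47%. If reversed: 513/(513 + 456) = 53%.

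**5. Effect of pooling on a rate.** Pooled rate = 0.5 × rate in naive patients + 0.5 × rate in previously exposed patients. The event rates below are assumed; the documents give none.

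- 2% in naive patients, 0% in exposed: pooled 1.0%, half the first-exposure rate.
- 2% in naive patients, 0.5% in exposed: pooled 1.25%, or 62.5% of it.

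**6. Which outcomes are touched.** The baseline asymmetry reaches TEAEs, laboratory values, blood pressure, pulse and ECG. It does not reach serious adverse events or discontinuations due to adverse events, although pooling would still mix the two histories there. Treatment-emergent antibodies are partly protected: Table CGAI.5.4 keeps Visit 3 as their baseline, and SAP 5.5.12.1.6 summarizes them for LY2951742-treated patients during LY2951742 treatment.

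**The case against.** The strongest reply is that the sections governing the tables already promise treatment groups in SP IV. If they apply, nothing is pooled and most of the columns requested here are already planned. That stands. A reader might infer that the sponsor has chosen to dilute first-exposure risks, but the documents support only an unresolved conflict in which pooling is one possible outcome.

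A reader might also infer that the SAP flatly contradicts the protocol. It does not quite do so: protocol 9.2 leaves discretion, and the SAP states that it supersedes the protocol. Neither fact settles a conflict inside the SAP.

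The +88% invites the reading that exposure differs widely throughout SP IV. It applies to one arm, between the Visit 7 and Visit 8 doses, under simple kinetics and an approximate half-life. It is an illustration only. Splitting by prior arm also does not deal with the two-fold dose choice open to investigators from Visit 9.

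Finally, first-exposure risk is not lost to the trial. Both active arms start with 240 mg at Visit 3, so SP III observes about 570 first exposures against about 570 concurrent placebo patients, with hypersensitivity and injection-site events tabulated by group. This limits the harm. It does not report the former placebo patients' own first exposure. The combined SP III/IV comparison is no substitute, because its placebo arm mixes placebo and active time and Table CGAI.5.4 gives no TEAE baseline for that combined period.

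**Conclusion.** The point holds as a conflict to be resolved and a rationale that fails. Having the same Visit 7 dose does not make the prior arms comparable for treatment-emergent outcomes: about half the group (47% to 53% under the dropout patterns tried) is drug-naive, and the baselines absorb on-drug events for the other half only. Unlike the carry-over, the difference in baselines does not fade over later visits.

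If the single-group sentence governs, a risk confined to first exposure would appear at about half its rate. That factor rests on the planned allocation and similar entry into SP IV across arms. If the other sections govern, there is no dilution. The primary and key secondary analyses are unaffected, and SP IV safety is descriptive and uncontrolled either way.

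**What to change.** In SAP 5.5.1.4, delete the single-group sentence with its same-dose rationale. State instead that SP IV disposition, exposure and safety (TEAEs including hypersensitivity and injection-site events, laboratory values, vital signs, weight, ECG and antibodies) are shown descriptively by prior double-blind treatment, with a total column. The minimum acceptable split is drug-naive versus previously exposed.

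Reconcile this with 5.5.2, 5.5.9, 5.5.10.3, 5.5.12.1 and protocol 9.2. Say whether prior treatment means the randomized group (protocol 9.2) or the modal group (later paragraph of 5.5.1.4).

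Cost: SAP wording and three extra columns per table. The treatment variable and data already exist, the pooled total is kept, and neither the design nor any treatment rule changes.
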